**Varenicline Adherence.**

At each session after Pre-Quit until end of treatment, participants are evaluated in terms of their adherence by self-report and pill count. At Weeks 3 (steady-state) and 12 (end of treatment), participants will be asked to provide blood samples to evaluate varenicline levels as a measure of adherence. Specific strategies to address non-adherence will be used if necessary. The varenicline adherence approach formally assesses participant reasons for non-adherence using scenarios and uses specific strategies to enhance compliance. If the participant discontinues study medication for any reason for 14 or more consecutive days prior to an adherence blood draw, the blood draw will not be conducted.

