## DRUGS OR DEVICES

#### *Study Medication*

##### *Dosing*

Varenicline will be used in accordance with FDA approved labeling: Day 1-Day 3 (0.5mg once daily); Day 4-Day 7 (0.5mg twice daily); and Day 8-Day 84 (1.0mg twice daily).

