#### Supply, Preparation, Storage, Packaging and Dispensing of Study Medication

Varenicline and matching placebo, provided at no-cost by Pfizer, will be packaged and stored at the University of Pennsylvania Investigational Drug Service. Varenicline and matching placebo will be packaged into blister packs in 1-2 week supplies. Medication will be distributed to participants in increments at Weeks 0, 3, and 7.

IDS will oversee the randomization and labeling of all study medication, and will assign each kit, which contains 12 weeks of medication for one subject, and a unique Pharmacy Randomization Number (PRN). Once a new subject is enrolled and eligible, IDS will assign the subject the next available PRN. The research staff will then label the blister packs with the subject's study ID number. The PRN and study ID number must match for each blister pack a subject receives. Medication kits will be stored in a locked cabinet at our center until they are dispensed at participant medication pick-up visits.

Regular study drug reconciliation will be performed to document drug assigned, drug consumed, and drug remaining. This reconciliation will be logged on the drug reconciliation form, and signed by the research staff member who completed the reconciliation.

At the completion of the study, there will be a final reconciliation of drug shipped, drug consumed, and drug remaining. This reconciliation will be logged on the drug reconciliation form, signed and dated by the research staff. Any discrepancies noted will be investigated, resolved, and documented prior to return or destruction of unused study drug. Drug destroyed on site will be documented in the study files.

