### **Behavioral Counseling (Week 0-Week 9).**

All subjects will receive manual-based counseling from a counselor trained and supervised by [name]. The counseling protocol is based on PHS guidelines for smoking cessation treatment (Fiore et al., 2008), used in our studies with cancer patients ([name] et al., 2010a) and the general population of smokers ([name] et al., 2010b; R01 DA025078). Counseling is included given its efficacy at helping smokers quit (Fiore et al., 2008).

to ensure that participants in the placebo arm receive active treatment to quit smoking and to increase study retention. Counseling is provided to both treatment arms until Week 9 to equate for time and attention across arms since this method was used in past varenicline trials (e.g., Gonzales et al., 2006). Counseling will be provided in-person at the CIRNA. Sessions can be arranged at convenient times for the participants, including evenings.

**Pre-Quit Session (Week 0):** The counseling program begins at Week 0 with a 1-hour in-person “pre-quit” counseling session to prepare for the target quit day. This session focuses on reviewing the participant’s history and experience with quitting as well as beliefs about smoking, quitting and perceived barriers to cessation. A quitting plan is initiated and involves identifying smoking triggers and strategies to increase the chance for success, including relying on social support to quit smoking and altering behaviors associated with smoking. The first 3 weeks of medication is dispensed at this session and will begin at the session or immediately following the session.

**Quit Day Session (Week 1):** At Week 1, participants will receive a 30-minute in-person “quit-day” session to review the initial quit attempt, identify potential reasons for relapse, and review a plan for avoiding tempting situations.

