**Table 2: Study Measures/Events**

Study Week	-1	0	1	3	5	7	9	12	18	24
Session Name	Intake	Pre-Quit	TQD	W3	W5	W7	W9	W12	W18	W24
TREATMENT										
Varenicline/Placebo		X	X	X	X	X	X	X	X	
Counseling		X	X	X	X	X	X			
SCREENING/COVARIATES										
Urine Pregnancy Screen	X									
Breath Alcohol Concentration	X									
Blood Pressure	X	X	X	X	X	X	X	X	X	X
Depression/Anxiety (HADS)	X	X	X	X	X	X	X	X	X	X
Demographics	X									
Smoking History/FTND	X									
ETOH History	X									
Medical History	X									
Psychiatric History (MINI)	X		X g							
Adherence to Antiretrovirals Instrument		X			X		X	X	X	X
Pharmacy Refill Data		X d			X d			X c		X c
Concomitant Medications	X	X	X	X	X	X	X	X	X	X
Creatinine Clearance	X a									
Viral Load Assessment								X e		
Nicotine Metabolite Ratio	X									
Genetic Polymorphisms	X									
Bipolar Disorder Symptoms (MADRS f , YMRS, Additional Screener, MINI) g	X		X	X	X	X	X	X	X	X
MEDIATING VARIABLES										
Affect (PANAS)		X	X	X		X		X		
Cognitive Function (N-back, CPT)		X	X	X				X		
Nicotine Withdrawal (MNWS-W)		X	X	X		X		X		
Smoking Urges (QSU-B)		X	X	X		X		X		
TREATMENT VARIABLES										
Adherence (Pill Count)			X	X	X	X	X	X		
Adherence (Blood)				X i				X i		
Side Effects Checklist (SEC)		X	X	X	X	X	X	X	X	X
Side Effects (Open-Ended)			X	X	X	X	X	X	X	X
Suicidality (C-SSRS)	X	X	X	X	X	X	X	X	X	X
OUTCOMES										
Carbon Monoxide (CO) Test	X	X	X	X	X	X	X	X	X	X
Smoking Rate (TLFB)		X	X	X	X	X	X	X	X	X
Urine Cotinine								X b	X b	X b
Quality of Life (HAT-QoL)		X	X	X	X	X	X	X	X	X
ACASI-SHQ h				X		X		X		
HVTN Social Impact Assessment h				X		X		X		
Client Evaluation Form h								X		

\*TQD = Target Quit Day

\*W= Week

\*Note: Target Quit Day visit may occur +3 days from target date; Week 3, 5, 7, 9, 12, 18, and 24 visits may occur +/- 1 week from target date.

a Will only be completed on initially eligible participants who have not had this test within last 6 months.

b Will only be completed on participants who self-report abstinence for  $\geq$  7 days prior to the assessment.

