#### Treatment Measures.

##### Varenicline Adherence

Varenicline adherence will be assessed by self-report using a time-line follow-back procedure and by pill count and the collection of used blister packs at each visit during the treatment period as done in past varenicline trials (e.g., Gonzales et al., 2006; Jorenby et al., 2006; Ebbert et al., 2009). We will also collect blood samples (10 mL) at Weeks 3 and 12 to assess varenicline levels as an additional measure of adherence and to examine the validity of self-report and pill count data. An adherence covariate will represent the proportion of total dose taken. These biosamples will be shipped to the laboratory of [name] at the University of California San Francisco for analysis. These blood samples will not be collected if the participant has not taken the study medication for 14+ days.

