### **Data Analysis**

[name] will oversee analyses which will be conducted using Stata, SAS, or R-Language software. Preliminary analyses will assess sample characteristics by treatment with chi-square or logistic regression (e.g., gender, dependence, depression). These variables will also be examined for their relationship to completion of outcome assessments. Variables related to treatment arm or completion of follow-ups will be included as covariates in analyses of study aims. Compliance measures will be evaluated across treatment arms, and controlled for in primary analyses. We will examine the correlation between self-report and pill count data and week 3 and 12 varenicline levels. Although we will use intent-to-treat as the primary method for

[figure not shown]
evaluating study aims, we will conduct a completers only analysis of study aims and examine study aims with participants lost to follow-up due to death excluded as done previously ([name] et al., 2003).

**Missing Data:** We will examine if the rate of missing data, primarily our smoking cessation outcome data, is related to a range of potential variables, including treatment arm allocation and HIV/AIDS-related, demographic, and smoking-related variables. Standard statistical methods will be used to identify possible correlates of missing data such as chi-square and regression. Variables found to be associated with the rate of missing data ( $p < .05$ ) will be included as covariates in the analyses of aims. In the event of items missing at random on measures, items will be imputed prior to calculating final scores using conditional means, estimated with an iterated version of Buck's method (Gleason & Staelin, 1975). Dropout and missed sessions present a more serious issue. The best way to deal with this is to avoid the problem in the first place by keeping subjects connected to the trial and motivated to complete measures. In our clinical trials, compliance and retention rates were >80% thanks to our close monitoring of participants and use of incentives to offset travel costs ([name] et al., 2008). Primary analyses will assume that all subjects for whom smoking outcome data are unavailable are smokers (intent-to-treat). This assumption, which is conventional in smoking cessation research, can attenuate the differences between study groups in quit rates. Thus, we will also conduct a "completers-only" analysis.

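### The Week 12 varenicline level can be drawn 7 to 8 days after the last scheduled dose, so visit date adds noise to its planned correlation with self-report and pill count

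*Combined protocol and SAP*

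**What the plan says.** Dosing (Drugs or Devices) gives the last step of the schedule as "Day 8-Day 84 (1.0mg twice daily"), and the treatment section under Study Procedures repeats it. The supply section describes "each kit, which contains 12 weeks of medication for one subject". Medication starts at Week 0: in the counseling section, the first supply "will begin at the session or immediately following the session".

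The adherence blood is scheduled "At Weeks 3 (steady-state) and 12 (end of treatment"), when "participants will be asked to provide blood samples to evaluate varenicline levels as a measure of adherence". The note to Table 2 says that "Week 3, 5, 7, 9, 12, 18, and 24 visits may occur +/- 1 week from target date". The Varenicline Adherence text under Study Procedures, the text of the same name under Treatment Measures, and footnote i of Table 2 all carry one restriction: no draw if the participant has been off study drug for 14 or more days.

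Treatment Measures gives the purpose of the levels as an additional adherence measure and "to examine the validity of self-report and pill count data". It defines the adherence covariate as the proportion of the total dose taken. Data Analysis says that the trial will "examine the correlation between self-report and pill count data and week 3 and 12 varenicline levels". The Aim 2 analysis adds that, if tenofovir users have more or worse side effects, mediation by plasma level can be explored.

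**The concern.** A drug level supports a judgement about adherence only if the time since the last dose is short or known. At Week 3 the participant is still dosing anywhere in the visit window. At Week 12 the schedule itself stops the drug at the target date, and the window runs on for another week. A draw inside that week reflects how late the visit was as well as how much drug was taken. The plan sets no maximum interval since the last dose and no adjustment for it.

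What is at stake is the objective check on self-report and pill count. A late but permitted visit can pair a complete and truthful pill count with a much reduced level. That pulls the Week 12 correlation down for a reason unrelated to the accuracy of the reports. The same noise would enter the exploratory tenofovir mediation if Week 12 levels were used.

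**Working it through.** **Calendar.** The plan's figure reproduces: 12 weeks x 7 = 84 days, which matches the Day 84 end of dosing and the 12-week kit. Day 1 is at or just after the Week 0 session, so the Week 12 target is Day 84 or Day 85, depending on how the days are counted.

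- Target Day 84: window Day 77 to Day 91. The latest visit is 7 days after Day 84, and 7 of 15 permitted days fall after dosing ends.
- Target Day 85: window Day 78 to Day 92. The latest visit is 8 days after Day 84, and 8 of 15 permitted days fall after it.

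Both 7 and 8 are below 14, so the off-drug rule does not stop these draws.

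**Remaining drug.** The documents state only that varenicline is renally cleared. The half-life is therefore an assumption, shown over a range with first-order elimination: share remaining = 2^(-24d/h), where d is days since the last dose and h is the half-life in hours.

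| Assumed half-life | 1 day | 3 days | 7 days | 8 days |
|---|---|---|---|---|
| 12 h | 25% | 1.6% | 0.006% | 0.002% |
| 24 h | 50% | 12.5% | 0.8% | 0.4% |
| 48 h | 71% | 35% | 8.8% | 6.3% |
| 72 h | 79% | 50% | 19.8% | 15.7% |

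For example, at 24 h and 7 days: 2^(-168/24) = 2^(-7) = 0.8%.

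**A bound from the plan's own label.** The plan calls Week 3 steady state. Take that to mean at least 95% of plateau. By the Week 3 target there have been about 14 days at full dose, so h is at most 14 x 24 / log2(20) = 77.7 hours, and the 7-day share is at most 2^(-168/77.7) = 22%. If the label also holds at the earliest permitted Week 3 visit (about 7 days at full dose), h is at most 38.9 hours and the share at most 5%. The 95% criterion is also an assumption, but on that reading at least 78% of the level is gone at 7 days.

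**On-time visits.** Summing the scheduled doses (assumed at 08:00 and 20:00, with a noon draw), the Day 85 level relative to the on-treatment trough is 0.79 at 12 h, 0.89 at 24 h, 0.94 at 48 h and 0.96 at 72 h. By Day 88 it is 0.01, 0.11, 0.33 and 0.48; by Day 91 it is 0.00, 0.01, 0.12 and 0.24. The distortion comes from late visits. A draw on Day 84 or 85 is little affected.

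**Where the levels go.** The correlation in Data Analysis names the Week 12 level and has no term for time since last dose. The mediation text under Aim 2 does not say which week's level it would use.

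**The case against.** Several stronger readings are tempting, and the documents do not support them.

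- A reader might infer that late attenders will be labelled non-adherent or have their self-reports overruled. No concentration cut-off is set anywhere, and nobody is classified by level. The stated use is a correlation across participants.
- A reader might infer that late visits put adherent people near zero. That depends on the assumed half-life and fits only the end of the window. At 1 day late the table leaves 25% to 79%.
- A reader might infer that about half the participants are affected. The 7 or 8 of 15 counts calendar days. The documents give no distribution of visit dates, so the affected share is unknown.
- A reader might infer that the tenofovir mediation is compromised. It is conditional and exploratory, and the Week 3 level is equally available for it.
- A reader might infer that the primary analysis is at risk, because Data Analysis controls for compliance measures there. The only adherence covariate defined is the proportion of total dose taken, and abstinence is judged by self-report and urine cotinine.

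It is also fair to say that the plan does anchor the draw: it is placed at end of treatment, which nominally coincides with the last dose. What is missing is a rule for late visits. The medication timeline follow-back that could supply the last-dose date is already collected, although no use of it for this purpose is stated.

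These points limit the reach of the concern. They do not remove it, because the Week 12 correlation is a stated analysis and would run on unadjusted levels.

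**Conclusion.** The point holds as a limited flaw in a supporting analysis. From the documents alone, a fully adherent participant can be sampled 7 to 8 days after the last scheduled dose and still be within window and within the 14-day rule. Under an assumed half-life of 12 to 48 hours, 0.01% to 9% of the level is left at 7 days and 1.6% to 35% at 3 days; at 72 hours the 7-day figure is about 20%. Week 12 levels will therefore vary with visit date at full adherence, and the correlation with self-report and pill count will be weakened. By how much cannot be computed without the spread of visit dates.

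The Week 3 sample, the proportion-of-dose covariate as defined under Treatment Measures, and the primary abstinence outcome are untouched. This is a cheap improvement, with no bearing on the trial's main conclusion.

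The timing rests on the consistent text that dosing stops at Day 84. Table 2, as it reads here, also marks Varenicline/Placebo at Weeks 12 and 18. Those marks may be an artefact of text extraction, but they conflict with the Day 84 end and the 12-week kit, and the passages must be reconciled.

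**What to change.** 1. In Varenicline Adherence and footnote i of Table 2, require the date and time of the last dose to be recorded at each adherence draw, using the timeline follow-back already collected.
2. In Data Analysis, pre-specify that Week 12 levels from visits after scheduled dosing has ended are excluded from the level-based adherence and mediation analyses, or are modelled with time since last dose. Word the rule so that on-time visits at Day 84 or 85 are kept.
3. Where possible, book the draw on the early side of the existing window. Do not make Day 84 a mandatory limit: that could catch on-time Day 85 visits, or force an earlier or second visit.
4. State which week's level the tenofovir mediation would use.
5. Reconcile the Week 12 and Week 18 treatment marks in Table 2 with the Day 84 end of dosing.

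Nothing here changes dosing or the visit window for the smoking outcome. The cost is a recorded last-dose date and time and a short analysis rule, with no added visit or sample. The downside is that some late Week 12 samples are lost to these analyses or need adjustment.

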**Mid-treatment Assessments.**

Assessments will be conducted at Weeks 0, 1, 3, 5, 7, and 9 by trained RAs to assess mediating variables and monitor safety. These assessments will take ~30 minutes to complete and will be done in-person prior to counseling. Assessments include measures of mediating variables (e.g., affect), HAART adherence, varenicline adherence (pill count and collection of blister packs), concomitant medication review, QOL, carbon monoxide assessment, and smoking behavior.

**Cognitive Function.**

We will assess cognitive function using validated computerized tasks as in our past varenicline study (Patterson et al., 2009). We will use the Visual/Spatial-N-Back task of working memory (Ehlis, Bahne, Jacob, Herrmann, & Fallgatter, 2008; Green et al., 2005; Owen, et al., 2005) and the PENN Continuous Performance

Task (P-CPT) of sustained attention (Kurtz et al., 2001). These tasks will be administered on a computer during Pre-Quit, Target Quit Day, and Weeks 3, 7, and 12.

### **Side Effect Monitoring.**

The research team has a clinical psychologist and physician to review initial eligibility and to monitor and address side effects during the trial. To reduce risk for adverse events, we will carefully assess eligibility to ensure that individuals with pre-existing conditions that can increase adverse event risk are excluded.

We will also frequently assess participant treatment reactions with established symptom checklists and validated suicidality and depression/anxiety scales. These assessments, as well as blood pressure assessments, are conducted at each visit before, during, and after the 12 week treatment phase by a research staff member.

We will use an established coding and reporting system for side effects also used in our ongoing varenicline trial (DA020830). In this system, personnel are trained to administer side effects measures, including validated scales of suicidality. If a side effect report or a score on an established scale indicates a safety concern, Drs. [name], [name], [name], and [name] will be notified per the Safety Monitoring and Reporting Protocol and will assume responsibility for the determination of a course of action (e.g., continue to monitor, stop medication). Participants are given contact information so that, if an adverse event occurs, they can contact study staff 24-hours a day. These side effects are also coded and managed by Drs. [name], [name], [name] and [name]. Serious adverse events are reported to the IRB, Pfizer, NIDA, and FDA in accordance with DSMP reporting procedures and participants may be referred to a PENN out-patient department or to the ER.

There are no known HAART/varenicline drug interactions (Drach et al., 2010). Varenicline is renally cleared, while the non-nucleoside reverse transcriptase inhibitors, protease inhibitors, raltegravir, and maraviroc are hepatically cleared. The nucleoside reverse transcriptase inhibitors (NRTIs) are metabolized by the kidney and, among the NRTIs, tenofovir is the only one related to risk for nephrotoxicity. HAART use will be assessed throughout the trial and patients on tenofovir will be closely monitored. We will examine the relationship between tenofovir use and varenicline side effects, including the assessment of varenicline plasma levels as a possible mediator of this relationship.

### **Outcome Assessments.**

The primary outcome variable for Aims 1 and 3 is 7-day point prevalence abstinence at Weeks 12 and 24, biochemically-confirmed with urine cotinine (Hughes et al., 2003). Secondary outcomes for Aim 1 include: biochemically-confirmed 7-day point prevalence abstinence at Week 18, smoking rate at Weeks 12, 18, and 24 for non-abstainers, prolonged abstinence to Weeks 12, 18, and 24, continuous abstinence at Weeks 12, 18, and 24, time to 7-day relapse (no grace period), and lapse and recovery events. For Aim 2, since individuals with HIV/AIDS who smoke report a lower QOL (Webb et al., 2007), we will closely monitor QOL, as measured by a commonly-used self-report scale for this population, and administer a checklist of varenicline-related side-effects.

Based on enrollment date, subjects will complete social impact assessments as part of a sub-study in collaboration with the Treatment Research Institute. Two assessments administered at Weeks 3, 7, and 12, include the self-administered, computer based ACASI-SHQ and the staff administered HVTN Social Impact Assessment. An additional client evaluation form is completed by participants at Week 12. Participants who miss administration sessions may complete the assessments at their subsequent study session.

Participants who are unable to quit smoking may be given referrals for smoking cessation treatment following the Week 24 assessment.

**Note:** If a participant is unable to complete a session in-person, assessments and counseling may be completed over the telephone. Participants will receive compensation for their time at the following in-person session.

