## OBJECTIVES

### 1. Overall Objectives

**Aim 1: Compare 12-weeks of varenicline treatment and behavioral counseling to 12-weeks of placebo treatment and behavioral counseling for treating nicotine dependence among individuals with HIV/AIDS.** Hypothesis: Varenicline and counseling will significantly increase end-of-treatment (week 12) and 24-week biochemically-confirmed 7-day point prevalence abstinence, vs. placebo and counseling.

**Aim 2: Assess effects of varenicline therapy on quality of life (QOL) and varenicline-associated side effects.** Hypothesis: QOL will be rated higher in the varenicline and counseling group vs. the placebo and counseling group, and there will be no significant differences between treatment arms in terms of the frequency of severe varenicline-related side effects.

**Aim 3: Assess changes in affect and cognitive performance as mediators of varenicline therapy's effect on quit rates.** Hypothesis: Improved affect and reduced cognitive impairment will mediate the effect of varenicline therapy on quit rates.

**Exploratory Aim: Explore participant-related variables as moderators of varenicline therapy's effect on quit rates.** To generate new hypotheses, we will explore participant-related variables as moderators of varenicline therapy's effect on quit rates, including socio-demographic (e.g., gender, race), psychiatric (e.g., depression), and medical (e.g., HIV/AIDS symptoms, method of HIV transmission) variables. Variables were selected for this analysis based on their relationship with smoking behavior (e.g., Webb et al., 2007).

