### **Other Smoking Measures (secondary)**

As per recommendations (Hughes et al., 2003), secondary smoking outcomes include: prolonged abstinence to Weeks 12 and 24 (relapse is 7 consecutive days of self-reported smoking, after a 2-week grace period), continuous abstinence at Weeks 12 and 24 (no smoking between the quit day and the follow-up; no smoking during weeks 9-12 as measured in previous varenicline trials with the general population of smokers; Gonzales et al., 2006), time to 7-day relapse (no grace period), smoking rate, and lapse (smoking episodes not lasting 7 days) and recovery (return to 24-hour abstinence) events (see [name] et al., 2010b). Abstinence and smoking rate outcome will also be available for Week 18.

**Cessation/Smoking Rate:** Daily smoking (presence and rate) will be assessed at each visit after Intake Session with the well validated timeline followback method (TLFB). These data can be used to assess the timing and rates of lapses (smoking episodes not lasting 7 days), recovery events (return to abstinence), and relapse events, as well as to monitor changes in smoking rates (i.e., # cigarettes/day). These data will also be used to compute and assess secondary measures of smoking cessation (e.g., continuous and prolonged abstinence).

**Carbon Monoxide (CO) Test:** Carbon monoxide will be measured at Intake and all subsequent visits to confirm smoking status.

**NicAlert™ Urine Dipstick (cotinine assessment):** Smoking status will be assessed with NicAlert™ urine dipsticks from Nymox Pharmaceutical Corporation

([http://www.nymox.com/products/nicalert/product\\_insert\\_for\\_urine.html](http://www.nymox.com/products/nicalert/product_insert_for_urine.html)). A midstream urine sample of approximately 25mL will be used to test for the presence of cotinine. Results will appear in one of seven category levels of usage. Level 0 indicates no detectable tobacco use; levels 1-2 indicate presence of cotinine, but as a non-user, and levels 3-6 indicate cotinine consistent with tobacco use. Participants with results in levels 3-6 will be considered smokers. The NicAlert™ urine cotinine assessment will be used to verify smoking status at Weeks 12, 18, and 24.

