## **2. Statistical Analysis**

### **Power**

Power is provided for the primary aims since the exploratory aim is hypothesis generating. Power calculations were all approximated as t- or z-tests (2-sided,  $\alpha = .05$ ), and conducted using PASS Software (Power and Sample Size, NCSS Software, Kaysville, UT).

Aim 1: The primary analysis is a comparison in week 12 and 24 cotinine-confirmed 7-day point prevalence quit rates between placebo and varenicline. For the week 12 comparison, we based our sample size selection on the expectation that quit rates in the placebo and varenicline arms would approximate those reported in past varenicline trials with the general population of smokers (i.e., placebo = 21.2%; varenicline = 50.3%; Gonzales et al., 2006). With a sample of 310, we have >90% power to detect a significant effect between our treatment arm. Notably, we have 80% to detect a difference in week 12 quit rates if the difference between treatment arms is as small as 15%, not 29% as found in Gonzales et al. (2006), since the effect for varenicline may be smaller in this sub-group of smokers. For the week 24 comparison, we based our sample size on the expectation that the quit rate in the placebo arm would be 14.5%, vs. 33.5% for varenicline (Gonzales et al., 2006). In this case, we have 85% power to detect a significant difference between treatment arms. However, we have 80% power to detect a difference between treatment arms if the treatment arm difference is only 15%, not the 19% reported in Gonzales et al. (2006), since the effect for varenicline may be smaller in this sub-group of smokers. Even though it may appear that we are over-powered for Aim 1, we require the proposed sample to conduct the non-inferiority analyses for Aim 2.

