**Aim 1: Compare 12-weeks of varenicline treatment and behavioral counseling to 12-weeks of placebo treatment and behavioral counseling for treating nicotine dependence among individuals with HIV/AIDS.** We will analyze quit rates using mixed effects logistic regression. The model will include a term for time-point and, possibly, a *small number of covariates as needed*. The hypothesized effect of treatment arm (placebo vs. varenicline) will be tested by including a dichotomous term for treatment arm; we will also test for an interaction between time-point and treatment. Outcomes of the logistic regression analyses will be characterized by odds ratios (e.g., odds of quitting smoking) and 95% confidence intervals. Although quit-rates at the end of 12 and 24 weeks will represent our primary outcome variables, similar logistic regression analyses will be performed for other measures of quit rates, including prolonged and continuous abstinence. In addition, many participants will fail to become completely abstinent, but may show a reduction in smoking. A secondary analysis will examine the effect of treatment arm on daily cigarette counts using mixed effects negative-binomial regression. Likewise, time to (recurrent) event models will be fitted using Cox regression, stratified by event sequence, as in [name] et al. (2010b), to assess lapse and recovery events over 24 weeks.

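### The population for the smoking-rate outcome is not settled, and a between-arm comparison limited to non-abstainers would not be randomised and could be biased

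*Combined protocol and SAP*

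**What the plan says.** Three places in the combined protocol and SAP bear on this outcome, and they do not match.

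- **Study Procedures, Outcome Assessments** lists among the Aim 1 secondary outcomes the "smoking rate at Weeks 12, 18, and 24 for non-abstainers".
- **Other Smoking Measures (secondary)** names the outcome with no restriction, in the run "time to 7-day relapse (no grace period), smoking rate, and lapse (smoking episodes not lasting 7 days".
- **Data Analysis, Aim 1** says: "A secondary analysis will examine the effect of treatment arm on daily cigarette counts using mixed effects negative-binomial regression". It names no analysis population. The motive it gives is that "many participants will fail to become completely abstinent, but may show a reduction in smoking".

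Abstinence, which defines the restricted group, is also the trial's primary outcome. The hypothesis in Overall Objectives is that "Varenicline and counseling will significantly increase end-of-treatment (week 12) and 24-week biochemically-confirmed 7-day point prevalence abstinence". For Week 12 the Power section assumes "placebo = 21.2%; varenicline = 50.3" (percent). For Week 24 it assumes "the quit rate in the placebo arm would be 14.5%, vs. 33.5% for varenicline".

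Nowhere is the non-abstainer comparison called descriptive. The plan does not say that abstainers enter the count model as zero, and it offers no method for selection by abstinence status.

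**The concern.** Randomisation makes the two arms comparable as randomised. It does not make the participants still smoking at Week 12 comparable, because the drug is expected to change who is in that group. If the odds of quitting depend on how much a person would otherwise smoke, the remaining smokers in each arm are differently selected. Their mean consumption can then differ although the drug has done nothing to it, and a real effect on continuing smokers can be distorted.

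At stake is the trial's only planned evidence on reduced smoking short of quitting. Because the population is stated in one place, omitted in another and left open in the analysis text, the choice could also be made after the data are seen.

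**Working it through.** **1. Inputs from the plan.** Total sample 310, with half to receive varenicline (Risk/Benefit Assessment), so 155 per arm. Quit rates are 21.2% and 50.3% at Week 12, and 14.5% and 33.5% at Week 24. The plan gives no power figure for the smoking-rate outcome, no baseline cigarettes/day, no relation between consumption and quitting, and no expected Week 18 quit rates.

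**2. Check on the quit rates.** The Power section says: "With a sample of 310, we have >90% power to detect a significant effect". With z = (|p1 − p2| − 1.96·√[2p̄(1 − p̄)/n]) / √[(p1q1 + p2q2)/n], n = 155 and p̄ = 0.3575, Week 12 gives (0.291 − 0.107)/0.0519 ≈ 3.55, or 99.98% power. That agrees with the statement. The stated 85% at Week 24 does not reproduce (97.8%). That is a separate matter and does not affect the use of the quit rates here.

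**3. Who remains in the restricted comparison.** Non-abstainers = 155 × (1 − quit rate).

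| Week | Placebo | Varenicline |
|---|---|---|
| 12 | 155 × 0.788 ≈ 122 (79%) | 155 × 0.497 ≈ 77 (50%) |
| 24 | 155 × 0.855 ≈ 133 (86%) | 155 × 0.665 ≈ 103 (67%) |

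**4. Size when the drug has no effect on continuing smokers.** These are assumptions, not figures from the documents: consumption has mean 12 and SD 8 cigarettes/day, is the same in both arms if still smoking, and the logit of quitting falls linearly in log consumption. The intercept is set in each arm to reach the planned quit rate. No baseline adjustment is made.

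- Gamma-distributed consumption, odds ratio of quitting 0.8 to 0.5 per SD: the Week 12 ratio of means among non-abstainers (varenicline/placebo) is 1.04 to 1.10. With quit rates of 21.2% and 36.2%, the 15-point difference the plan also considers, it is 1.02 to 1.05.
- Lognormal consumption, 2,000 simulated trials of 155 per arm, t-test on log cigarettes at two-sided 5%:

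| Odds ratio per SD | Week 12 ratio | Week 12 rejection | Week 24 ratio | Week 24 rejection |
|---|---|---|---|---|
| 1.00 | 1.00 | 4.5% | 1.00 | 5.0% |
| 0.78 | 1.04 | 7.7% | 1.03 | 6.2% |
| 0.61 | 1.08 | 15.7% | 1.05 | 10.6% |
| 0.37 (strong selection) | 1.14 | 41.9% | 1.09 | 25.5% |

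With no selection the bias vanishes, as it should. In the extreme case where only the lightest smokers quit, the ratios are 1.25 (Week 12) and 1.15 (Week 24).

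**5. When there is a real effect.** In this model the true ratio is multiplied by the spurious one. A true 20% reduction at Week 12 becomes 0.80 × 1.082 = 0.866 (about 13%) at odds ratio 0.61, and 0.80 × 1.138 = 0.910 (9%) at 0.37. The sign reverses only if the true reduction is below 1 − 1/1.04 ≈ 4% to 1 − 1/1.10 ≈ 9%.

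**6. Baseline adjustment.** If quitting depends on baseline consumption only, adjusting for log baseline returns the ratio to 1.00. If it depends on the consumption a person would have at follow-up, baseline is an imperfect proxy. Adjusted ratios then ran from about 1.00 to 1.11 over the settings tried, with about 1.05 to 1.08 in the middle of that range.

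**7. All randomised, abstainers as 0.** Lognormal model, odds ratio 0.61, Week 12: placebo 12.68 × 0.788 ≈ 10.0, varenicline 13.72 × 0.497 ≈ 6.8 cigarettes/day. In the same data the non-abstainer means, 12.7 and 13.7, point the other way.

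**The case against.** The restriction appears once, in an outcome list. The outcome definitions omit it, timeline follow-back is collected from everyone at each visit after Intake, and Data Analysis makes intent-to-treat the main approach to the aims. The count model may therefore already be meant for everyone. This stands as a limit: a reader might infer that the planned model is confined to non-abstainers, and the text does not establish that. Equally, the sentence introducing the model speaks of people who do not fully quit, so the broader reading is not established either.

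A reader might also infer that the trial will make varenicline appear to raise consumption. The documents do not support this. They give no relation between consumption and quitting; the reverse relation would favour varenicline; and under the assumed relation a real reduction of any size beyond a few percent is diluted rather than reversed.

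Baseline adjustment could remove the problem, and baseline smoking is collected. But the plan commits to covariates only as needed, or where they are related to arm or follow-up completion. Adjustment also works only if selection acts through baseline consumption.

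Finally, counting abstainers as 0 changes the question. The contrast becomes total consumption, including the effect through quitting, and where the drug does nothing for continuing smokers it largely restates the primary result. That is a genuine cost. The contrast is nevertheless one between randomised groups, which the non-abstainer comparison is not.

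**Conclusion.** The point holds in conditional form. The plan describes the population for this outcome inconsistently, and under the restricted description the between-arm comparison conditions on an outcome the drug is expected to change. It is free of this bias only if quitting is unrelated to how much a person would smoke, or if varenicline does not affect quitting; the latter contradicts the trial's hypothesis.

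Neither size nor direction can be read from the documents. The range of 1.04 to 1.10 at Week 12 rests on the assumed consumption distribution, on lighter smokers quitting more readily, and on an unadjusted analysis. This concerns one secondary outcome; the primary abstinence comparison is unchanged. It merits correction because the remedy is cheap, not because the trial's main conclusion is at risk.

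**What to change.** Reconcile Outcome Assessments, Other Smoking Measures and the Aim 1 analysis text, so that each says the following:

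1. The between-arm test is of cigarettes/day at Weeks 12, 18 and 24 in all randomised participants, with abstainers counted as 0, in the mixed effects negative-binomial model already planned, adjusted for baseline cigarettes/day.
2. A stated rule covers participants with no count. The Accrual section allows up to 20% to withdraw (0.20 × 310 = 62 people), and coding them as smokers supplies no number of cigarettes.
3. A stated rule covers participants who report zero but fail cotinine confirmation. They are classed as smoking while their recorded count is 0.
4. The non-abstainer figure is reported descriptively, also baseline-adjusted, and labelled as a non-randomised comparison.

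The cost is a few sentences plus the decisions on items 2 and 3. No new data are needed, since timeline follow-back and baseline smoking are already collected. The small downside is that the tested contrast measures total consumption rather than reduction among continuing smokers, and this should be said where it is reported.
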